8.3. Missing Data

To reduce the loss-to-follow-up risks: participant phone calls and review of hospital records for subjects with missing data will be performed. Currently there are no plans for attempting a multiple imputation analysis.

Harvard T. H. Chan School of Public Health

Massachusetts, USA

Study Identification

Unique Protocol ID: HeraInc

Brief Title: A Mobile Health Intervention to Increase Uptake of Prenatal Care in Syrian Refugee Population in Turkey

Official Title: A Mobile Health Intervention to Increase Uptake of Prenatal Care in Syrian Refugee Population in Turkey

Study Status

Study Start: October 1, 2021

Primary Completion: October 1, 2022

Study Completion: October 1, 2022

Sponsor/Collaborators

Sponsor: HERA Inc

Responsible Party: Sponsor

Collaborators: Medical Rescue Association (MEDAK), Turkey

Oversight

Human Subjects Review Board Status: Approved

Approval Number: 2021-04/04

Board Name: Acibadem Mehmet Ali Aydinlar University Medical Research

Institutional Review Board Email: [contact] Address:

Study Description

Brief Summary: The purpose of this study is to assess the effectiveness of mobile phone-based appointment reminder notifications sent through the HERA app in increasing the uptake of 4 WHO recommended prenatal visits among Syrian refugee population.

Detailed Description:

Background: 12 million Syrians have been forcibly displaced from their homes since the start of Syrian Civil War in 2011. Despite Turkey providing free healthcare services through national insurance to nearly 4 million refugees that it hosts, pregnant Syrian women are less likely to attend prenatal visits and more likely to die during and after labor. An

increase in the uptake of prenatal care may improve quality of life through healthy pregnancies and safer labor conditions in this population with double vulnerability.

Mobile phone-based reminders have been shown in randomized controlled trials and systematic reviews to increase the uptake of various services, including prenatal care. Mobile phone penetration is high among Syrian refugees in Turkey and qualitative studies demonstrate that mobile health interventions are acceptable and feasible for Syrian refugees.

Primary objective: To evaluate the impact of mobile phone-based reminders on the uptake of prenatal care among pregnant Syrian refugee women. More specifically, the study assesses the effectiveness of mobile phone-based reminders by measuring the percent increase in the number of prenatal appointments attended by intervention arm participants compared to the control arm participants.

Study design: This is a behavioral intervention study using an un-blinded, parallel group, randomized controlled study design.

Recruitment strategy: Participants will be enrolled from the obstetrics and gynecology department of refugee health clinics in Istanbul, Turkey with the help of a translator (Turkish to Arabic). The enrollment will take place with the help of the physician.

Primary Outcome: The primary outcome of this study is the number of medical visits, following the initial baseline PNC visit, over the 6-month period prior to childbirth.

Secondary outcomes: Secondary outcomes are based on the Sociodemographic and Health History form. The form gathers information about demographics of the participants (age, education, employment, marital status, number of children) and health history (previous pregnancies, delivery methods, miscarriages, stillborn, chronic conditions and medications. We will further examine these risk factors on the number of medical visits during the study period.

Conditions

Conditions: Prenatal Care, Pregnancy

Keywords: Mobile health, Refugee

Study Design

Study Type: Interventional

Primary Purpose: Health Services Research

Interventional Study Model: Parallel Assignment

The intervention group cluster will use the HERA application to receive appointment reminders. The Informed and Non-Informed Control groups will not be using the HERA application.

Number of Arms: 3

Masking: None (Open Label)

Allocation: Randomized

Enrollment: 162 [Anticipated]

Arms and Interventions

Experimental: Reminder

Participants will fill the sociodemographic and health history form. Participants will receive reminders in the form of push notifications for prenatal checkup dates automatically generated according to their pregnancy start data or initial check-up appointment for 6 months. Reminders will be sent at the following intervals: 1) 2 weeks before the appointment, 2) 1 day before the appointment, and 3) on the day of appointment. After this date, participants will receive push notifications asking whether they went to the appointment or not weekly for 1 month. This reminder algorithm will be used for each prenatal checkup for a total of four appointments: once in first trimester, once in second trimester and two in third trimester, using the World Health Organization and Turkish Ministry of Health prenatal checkup calendar. At the end of 6 months of follow up period, participants will be contacted via phone call to ask for any remaining appointments or unanswered notifications.

No Intervention: Informed Control No Reminder

Participants will fill the sociodemographic and health history form. Their contact information will be gathered. Participants will be contacted at the end of 6 months and will be asked about the number of the prenatal care appointments they have attended during their pregnancy.

No Intervention: Uninformed Control No Reminder

Participants will fill the sociodemographic and health history form. No contact information will be gathered. The purpose of this arm is to estimate the “true” baseline for the number of visits without any extra attention given by the medical staff.

Outcome Measures

Primary Outcome Measure: Rate of attendance for prenatal care visits: The number of 4 mandatory prenatal care appointments that are attended are presented here.

Secondary Outcome Measure: Sociodemographic and Health information form data: Data about sociodemographic and health information of participants will be presented here.

Eligibility

Minimum Age: 18 Years

Maximum Age: 49 Years

Sex: Female

Gender Based: No

Accepts Healthy Volunteers: Yes

Criteria:

Inclusion Criteria:

- Having the status of “Syrian under temporary protection”
- Being in the first trimester of the pregnancy
- Initial prenatal visit
- Age equal or greater than 18 years and less than or equal to 49

Exclusion Criteria:

- Having a citizenship or a status other than “Syrian under temporary protection”
- Not owning a mobile phone
- Being unable to read and write
- Not initial prenatal visit
- Having a chronic disorder or high-risk pregnancy that requires the individual to go to the hospital frequently. Frequently is defined as more than 3 visits post the baseline visit.
- While gestating, those that develop a high-risk pregnancy that requires more than 3 visits post the baseline visit.

Contacts/Locations

Central Contact Person: [name]

[contact]

Email: [contact]

Study Officials: [name]

Study Principal Investigator Founder/CEO

Sociodemographic and Health History Form (will be filled with the assistance of a translator)

1. Age:
2. What is your highest level of education?
 - a. Undergraduate
 - b. High School
 - c. Middle School
 - d. Elementary school
 - e. Can read
 - f. Can not read
3. Do you currently work? If yes, what is your profession?
.....

4. Are you married?

- a. Yes
- b. No

5. Is your spouse alive?

- a. Yes
- b. No

6. Does your spouse live with you?

- a. Yes
- b. No

7. How many children do you have?

- a.
- b. Doesn't have any

8. How old are your children?

Child 1 age:

Child 2 age:

Child 3 age:

Child 4 age:

Child 5 age:

If more add here:.....

9. Have you ever had a miscarriage?

- a. No
- b. Yes, time(s)
- c. If yes, do you remember during which week of your pregnancy?

.....

10. Have you lost any children?

- a. Yes, time(s)
- b. No

11. Did you ever give birth to a stillborn baby (at or after 28 weeks of gestation)?

- a. Yes, time(s)
- b. No

12. During your previous pregnancies, where did you give birth? (make sure to include all children)

- a. At home, time(s)
- b. At a hospital, time(s)

13. What type of delivery did you undergo? (make sure to include all children)

- a. Vaginal birth, time(s)
- b. C-sections, time(s)
 - i. If C-section, what was the reason (preference, medical emergency, etc.)?
.....

14. Have you been to prenatal care appointments during your previous pregnancy? If yes, how many appointments have you been to?

.....

15. Have you been diagnosed with a medical condition (diabetes, hypertension, asthma, etc.) that requires long-term medication use?

- a. No
- b. Yes, please specify
 - i. If yes, what's the name of the medication?
.....

16. For how long have you been living in Turkey?

.....

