Alternative hypothesis: Sending reminders on participants' upcoming appointments 2 weeks before, 1 day before, and on the day of the appointment will result in a percent increase on the number of appointments that are attended by the intervention group compared to the control groups.

6. Study Methods

6. 1. Study Type

This is a behavioral intervention study using an unblinded, parallel groups, randomized controlled study design. The intervention group ("Reminder") will download and use the HERA application to receive appointment reminders through push notifications. The control group ("No reminder") will not be using the HERA application, and therefore won't be provided with any reminders. The third group will also be a non-notified control group, i.e., "No reminder" as well.

The third group's data will be collected retrospectively via hospital records. The intent of the 3rd arm is to estimate the “true” baseline for the number of visits without any extra attention given by the medical staff, in order to prevent inadvertent behavior modification through perceived observation bias.

6. 2. Study Procedure

Pregnant Syrian refugee women who are in their first trimester of pregnancy will be enrolled in the study. Participants will be enrolled from the Obstetrics and Gynecology department of refugee health clinics in Istanbul. Participants will be randomized and enrolled into intervention or either of the two control arms (refer to section 6.5. Randomization Strategy for details).

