For the intervention arm, participants will be given the consent form. After having consented to participate in the study, they will be given the socioeconomic and health history form. In what follows, they will receive a 30-minutes brief about the mobile app HERA and will be asked to download it. The mobile application will automatically plan out the dates of further prenatal care appointments based on the date of the last menstruation. Participants will receive reminders in the form of push notifications for prenatal checkup dates for 6 months. Reminders will be sent at the following intervals: 1) 2 weeks before, 2) 1 day before and 3) on the day of the recommended appointment. After the recommended appointment date, participants will receive push notifications asking whether or not they went to the appointment in weekly intervals for 1 month. This reminder algorithm will be used for each prenatal checkup for a total of three appointments post the baseline visit: once in second trimester and two in third trimester, using the World Health Organization and Turkish Ministry of Health prenatal checkup calendar. At the end of 6 months of follow up time, participants in the intervention arm will be contacted via phone call to ask for any remaining appointments or unanswered notifications. Completeness of 3 prenatal care appointments post the baseline visit, as recommended by WHO and implemented by Turkish MoH will be compared to the control groups.

Participants in the informed control arm will be given the consent form and will be asked for their contact information if consented. They will also be given the socioeconomic and health history form. Participants in the non-informed control group just will be given the socioeconomic and health history form. Both the informed and non-informed control group members will be

reached out at the end of the 6-month study period to be asked about the number of prenatal care appointments they attended. If unable to be reached, retrospective chart review of the participant's medical record will be attempted, in order to obtain the number of attended prenatal care appointments.

6. 2. 1. Recruitment Strategy

Participants will be enrolled from the obstetrics and gynecology department of refugee health clinics in Istanbul, Turkey with the help of a translator (Turkish to Arabic). The enrollment will take place with the help of the physician.

6. 3. Study Population

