Subjects will be selected on the following basis: randomly select a week and recruit on 6 days of that week. On 3 of the days the selection process will start in the morning, denoted as AM, (the first part of the day that is expected to see half of the patients) and on the other 3 days the selection process will start in the afternoon, denoted as PM, (the second part of the day that is expected to see half of the patients.) For each AM/PM session, the first 27 subjects giving approval to be in the study will be randomly assigned into one of the 3 arms. It is estimated that 100 to 200 women use the hospital daily. Thus, we feel that most likely the daily target intakes will be met. However, if not met by the end of the AM/PM shift, the selection process will stop. After day 6 and before any data analysis, a check will be done on the sample sizes and additional subjects may be recruited by selecting another week to perform additional recruiting.

This sampling plan requires that the number of women coming to see the medical staff be approximately the same day to day and AM to PM.

Details of the random assignment to AM/PM and to groups are attached. The assignment of treatment and control groups to 0, 1 or 2 will be done prior to the start of subject recruitment but will not be shared with the data analyst until after the analysis is complete.

7. Outcomes

Primary Outcome:

The primary outcome of this study is the number of medical visits, following the initial baseline PNC visit, over the 6-month period prior to childbirth.

Secondary analyses:

In the secondary analyses, we will further examine other risk factors, including sociodemographic and reproductive medical history, on the number of medical visits during the study period. The following additional data will be gathered:

1. Age
2. Highest level of education
3. Current employment status and profession if employed
4. Marital status
5. If married, whether the spouse is alive or deceased
6. If married, whether the spouse resides with the participant or not
7. Number of children
8. Ages of children
9. Miscarriage history, and the number and the timing of miscarriage, if any
10. Number of deceased children, if any
11. Number of times the participant gave birth to stillborn baby, if any
12. If prior pregnancies, the number of deliveries occurred at home and at a hospital
13. Type of delivery (vaginal, C-section) and the number of each type

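### The arm code is hidden only from the data analyst; nothing masks the callers and chart reviewers who record the visit count, and the reminder-arm call reveals the arm

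*Combined protocol and SAP*

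**What the plan says.** **Masking.** SAP 6.1 states: "This is a behavioral intervention study using an unblinded, parallel groups, randomized controlled study design". The protocol's Study Design section agrees: "Masking: None (Open Label". SAP 6.5 adds one safeguard: the assignment of arms to codes 0, 1 and 2 is fixed before recruitment and "will not be shared with the data analyst until after the analysis is complete". No other role is kept from knowing the arm.

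**How the count is obtained.**
- *Reminder arm* (SAP 6.2; protocol, Arms and Interventions). After each recommended date the app asks weekly for one month whether the woman attended. At 6 months, "participants in the intervention arm will be contacted via phone call to ask for any remaining appointments or unanswered notifications".
- *Both control arms* (SAP 6.2). The women are "reached out at the end of the 6-month study period to be asked about the number of prenatal care appointments they attended". The next sentence gives the fallback: "If unable to be reached, retrospective chart review of the participant's medical record will be attempted".
- *Third arm* (SAP 6.1). "The third group's data will be collected retrospectively via hospital records". For this arm the protocol's Arms and Interventions section says that contact information is not collected.
- *Missing data, any arm* (SAP 8.3). "participant phone calls and review of hospital records for subjects with missing data will be performed".

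Neither document gives a call script common to the arms, a masked chart-review procedure, or a rule for a visit whose status is unclear.

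**The concern.** Masking the analyst protects the analysis. Here that is a pre-specified one-way ANOVA, which leaves little room for discretion. It cannot correct a count that was already affected by knowledge of the arm when it was written down. Women cannot be blinded to an app, but the people who record their visits largely can be.

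The caller's knowledge of the arm follows from the procedure itself: a call about unanswered notifications can only go to a woman in the reminder arm. The recorder also has some room for discretion, because the outcome is described in different ways: medical visits after baseline (SAP 7), completion of three post-baseline prenatal appointments (SAP 6.2), and attendance at four mandatory appointments (protocol, Outcome Measures).

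At stake is the credibility of a positive result. The sponsor, HERA Inc, bears the name of the app under test. That is no evidence of bias, but it is a setting in which masked recording is worth having.

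**Working it through.** **1. The passages side by side**

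| Person or route | Arm hidden? | Place |
|---|---|---|
| Data analyst | Yes, until the analysis is complete | SAP 6.5 |
| Caller, reminder arm | No; the content of the call reveals the arm | SAP 6.2; protocol, Arms and Interventions |
| Caller, control arms | Not stated | SAP 6.2 |
| Chart reviewer | Not stated | SAP 6.1, 6.2, 8.3 |
| In-app answers | Not applicable; the woman reports | SAP 6.2 |

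The gap in masking is therefore a matter of text. Its effect on the result is not, and can only be illustrated.

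**2. The plan's own figure**

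SAP 6.4 gives 40 per arm for effect size 0.33, 90% power and two-tailed 0.05. A three-group ANOVA with Cohen's f = 0.33 and N = 120 has noncentrality N × f² = 120 × 0.1089 = 13.07 and power 0.902, so 40 is reproduced when 0.33 is entered as f. Whether 0.33 should be used as f is a separate question on which nothing below depends.

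**3. Inputs for the illustration**

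- Target difference 0.5 visits and SD 1.5, the plan's stated maximum (SAP 6.4). SD 1.0 is an assumption, used as a lower value.
- Analysed per arm: 54 × 0.8 = 43.2, taken as 43 (54 enrolled, 20% loss, SAP 6.4).
- Test: three-arm one-way ANOVA at 5% (SAP 8.1).
- b = false credit per reminder-arm woman, in visits. The documents give no value; 0.1 and 0.2 are assumptions, equal to one extra visit per 10 or per 5 women.

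**4. Share of the target**

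0.1/0.5 = 20%; 0.2/0.5 = 40%.

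**5. False-positive rate**

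With no true effect and one arm shifted by b, the noncentrality is λ = n × (2/3) × b²/SD². The rejection rate is the probability that a noncentral F(2, 126, λ) exceeds the 5% critical value, 3.068.

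| SD | b | λ | Rejection rate |
|---|---|---|---|
| 1.5 | 0.1 | 43 × 0.6667 × 0.01/2.25 = 0.127 | 6.0% |
| 1.0 | 0.1 | 43 × 0.6667 × 0.01/1.00 = 0.287 | 7.2% |
| 1.5 | 0.2 | 43 × 0.6667 × 0.04/2.25 = 0.510 | 8.9% |
| 1.0 | 0.2 | 43 × 0.6667 × 0.04/1.00 = 1.147 | 14.3% |

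With 40 per arm the same calculation gives 5.9%, 7.0%, 8.6% and 13.6%. A two-arm comparison of reminder with one control, with SE = SD × √(2/43), gives slightly more (6.1% and 7.5% for b = 0.1; 9.5% and 15.3% for b = 0.2), but the plan does not specify that test.

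**The case against.** **Open label is unavoidable and is disclosed.** This is true of the women. It does not extend to whoever writes down the count.

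**Part of the reminder-arm count never passes through a caller.** This stands. Attendance is first reported in the app, and the 6-month call covers only what is left over. Masking callers cannot affect those answers, so a reader should not infer that masking would remove detection bias. Repeated prompts in one arm, a single recall question in another and hospital records in the third are differences in measurement in their own right.

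**Chart reviewers may be unable to favour the reminder arm.** This largely stands. SAP 6.1 and 6.2 tie chart review to the control arms; only SAP 8.3 extends it to any woman with missing data. On the narrower reading, an unmasked reviewer could miscount controls but could not credit the reminder arm.

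**No adjudication is described.** This also stands. A control woman is asked for a number, and the documents do not say that the recorder must decide what counts as a prenatal visit. Such discretion is possible under the differing outcome descriptions, but it is not prescribed.

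**A bias towards the app is not shown.** A reader might infer from the sponsor's interest that counts will be inflated in the reminder arm. The documents give neither a direction nor a rate, and that inference should not be drawn.

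**Conclusion.** The point holds in a limited form. Neither document hides the arm from the people who record the primary outcome, and the reminder-arm caller necessarily knows it. Unclear visits could then be counted differently by arm, and masking the analyst does not protect against that. It is one of several differences in ascertainment and may not be the largest.

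The figures (20% or 40% of the target difference; false-positive rate about 6-7% or 9-14%) rest on assumed false credits of 0.1 or 0.2 visits, SD between 1.5 and 1.0, 43 women per arm, normal errors and no true effect. They show what a modest miscount could do and are not an estimate of what will happen. No stated sample size or power figure changes. The change is worth making because it costs little, not because harm has been shown.

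**What to change.** Extend the SAP 6.5 rule to outcome recording.

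1. **Charts.** Give reviewers one list of study numbers with all arms mixed and no arm shown. Include reminder-arm women, so that being on the list does not reveal the arm.
2. **Calls.** At 6 months ask every woman called for her total number of visits first, in identical words, on a sheet without the arm. Use that count, not the in-app answers, for the primary comparison. Only then open the questions about notifications.
3. **Reconcile the follow-up of uninformed controls.** SAP 6.1 (hospital records), SAP 6.2 (contacted at 6 months, charts as fallback) and the protocol's Arms and Interventions section (no contact information) cannot all hold. The mixed list depends on the answer: if these women are followed by chart only, reminder and informed-control charts must be on the list too, at most 2 × 54 = 108 more.

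**Cost.** A revised list and call sheet, no extra assessor, a slightly longer reminder-arm call because it asks for a full count, and possibly the additional charts in step 3. Masking will be partial, since some women will mention the app unprompted.

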The population included in this study are pregnant Syrian refugee women between the ages of 18 to 49, who are in their first trimester of pregnancy.

6. 3. 1. Eligibility

Inclusion Criteria:

- Having the status of “Syrian under temporary protection”
- Being in the first trimester of the pregnancy
- Initial prenatal visit
- Age equal or greater than 18 years and less than or equal to 49

Exclusion Criteria:

- Having a citizenship or a status other than “Syrian under temporary protection”
- Not owning a mobile phone
- Being unable to read and write
- Not initial prenatal visit
- Having a chronic disorder or high-risk pregnancy that requires the individual to go to the hospital frequently. Frequently is defined as more than 3 visits post the baseline visit.
- While gestating, those that develop a high-risk pregnancy that requires more than 3 visits post the baseline visit.

6. 4. Sample Size Determination

The primary outcome measure for the power and size calculation is the difference in the mean number of visits among the different arms of the study. We set our target detectable difference in means to be 0.5 or more additional visits. As the maximum standard deviation is 1.5 due to the restricted range of 0 to 3 visits, our target effect size is $0.5/1.5 = 0.33$. Our calculation shows that each arm will need at least 40 patients to have a power of 90% and a two tailed significance level of 0.05. Due to the nature of refugees, we anticipate a high loss due to follow up and other reasons for dropout. Without prior information, we assume a 20% loss rate and therefore inflate the number of patients per arm by 25%. Thus, we plan to enroll 54 patients per arm for a total of 162 individuals. The statistical software G*Power Version 3.1.9.6 available from the UCLA Institute for Digital Research & Education Statistical Consulting website; [G*Power \(ucla.edu\)](http://G*Power (ucla.edu)), was used for the calculations.

6. 5. Randomization Strategy

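### The primary outcome is counted in two ways, three visits after baseline or four including it, and nothing says how the baseline visit is removed from control answers or chart counts

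*Combined protocol and SAP*

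**What the plan says.** Both documents enrol women at their initial prenatal visit, in the first trimester, so each woman has one visit on record at entry.

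**Baseline visit excluded**
- SAP section 7 defines the primary outcome as "the number of medical visits, following the initial baseline PNC visit, over the 6-month period prior to childbirth". The Primary Outcome paragraph in the protocol's Detailed Description agrees: "The primary outcome of this study is the number of medical visits, following the initial baseline PNC visit".
- SAP section 6.2 runs the reminder algorithm "for a total of three appointments post the baseline visit" and says that completion of these three will be compared with the control groups.
- SAP section 6.4 bases the sample size on a "restricted range of 0 to 3 visits".

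**Baseline visit included, or not excluded**
- The protocol's Outcome Measures state: "The number of 4 mandatory prenatal care appointments that are attended are presented here".
- The protocol's Arms and Interventions section lists four appointments for the reminder arm, the first of them in the first trimester.
- In the same section, informed controls are to be "asked about the number of the prenatal care appointments they have attended during their pregnancy".
- SAP section 6.2 has both control groups "reached out at the end of the 6-month study period to be asked about the number of prenatal care appointments they attended", with no limit to visits after baseline.

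The source of the uninformed control arm's count is also unsettled. SAP section 6.1 takes it retrospectively from hospital records, SAP section 6.2 has these women contacted at 6 months, and the protocol collects no contact information from them.

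**The concern.** The baseline visit is attended by everyone and reminders cannot affect it. It should therefore be out of the count in every arm or, at the least, treated identically in every arm. The documents ensure neither.

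The arms are also measured differently. Reminder-arm women answer app prompts appointment by appointment, with a closing call for anything outstanding. Controls give a single recalled total, with chart review if they cannot be reached. If the two instruments treat the first visit differently, the difference between arms contains a counting artefact as well as any effect of reminders. One visit is a large artefact against a target difference of 0.5.

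**Working it through.** **Inputs.** From SAP section 6.4: target difference 0.5 visits, SD 1.5, range 0 to 3, 40 per arm before dropout, two-sided 0.05, 90% power. From SAP section 8.1: one-way ANOVA on three arms. Assumed, because the documents do not give them: the share q of controls who include the baseline visit (full range 0 to 1 shown), and the control mean m of post-baseline visits (1.0, 1.5 and 2.0 shown).

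**The plan's own figures.** The largest possible SD on a 0 to 3 scale is 3/2 = 1.5, as stated, so the sample size was set on the post-baseline scale. The 40 per arm reproduces as a three-arm ANOVA with Cohen's f = 0.33 (power 0.902). Whether 0.5/1.5 is the right value to enter as f is a separate matter. Below, 40 and 1.5 serve only as the plan's stated values.

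**Scenario A: baseline visit counted by some controls and by no reminder-arm woman.** The control mean rises by q, so observed difference = 0.5 - q.

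| q | Observed difference when the true gain is 0.5 | ANOVA rejection probability when the true effect is 0 |
|---|---|---|
| 0 | +0.50 | 0.05 |
| 0.25 | +0.25 | 0.108 |
| 0.50 | 0 | 0.311 |
| 0.75 | -0.25 | 0.621 |
| 1 | -0.50 | 0.870 |

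The last column uses the noncentral F distribution with 40 per arm and the SD held at 1.5. The figures are the same whether one or both control arms carry the offset.

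**Scenario B: baseline visit counted in all arms.** Every mean rises by 1, so the difference and the ANOVA are unchanged. The percent increase falls from 0.5/m to 0.5/(m + 1):
- m = 1.0: 0.5/1.0 = 50% becomes 0.5/2.0 = 25%.
- m = 1.5: 0.5/1.5 = 33% becomes 0.5/2.5 = 20%.
- m = 2.0: 0.5/2.0 = 25% becomes 0.5/3.0 = 17%.

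**Scenario C: the analyst subtracts 1 from every control answer.** This is exact only if q = 1. Otherwise the share 1 - q who had already left the visit out are scored one too low, and the observed difference is 0.5 + (1 - q). At q = 0.5 that is 1.0, twice the true gain. This ignores answers of 0, from which 1 cannot be subtracted.

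**Scenario D: baseline visit excluded in all arms.** The offset is 0, and a true difference of 0.5 is observed as 0.5.

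**The case against.** A reader might infer that the plan, followed as written, loads a one-visit penalty on the reminder arm. The documents do not support that, for three reasons.

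- Leaving the baseline visit out of the reminder arm's count is SAP text only. The protocol's reminder-arm description includes a first-trimester appointment, so within the protocol the reminder schedule, the informed-control question and the Outcome Measures all include it. Within the SAP, the intended comparison excludes it. Scenario A needs the SAP's reminder arm paired with unrestricted control recall.
- It is also not a simple case of the protocol counting four and the SAP three. The protocol's Primary Outcome paragraph gives the same post-baseline definition as the SAP, so the protocol contradicts itself.
- The control question appears as a short description of the arm. The documents contain no call script or scoring rule, and an analyst who followed the post-baseline definition could subtract the visit.

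The dilution of the percent increase is secondary as well: SAP section 8 specifies no analysis of a percent increase, and the control means above are assumed.

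All of this stands, and it limits the claim to a contradiction with a possible bias. It does not remove the point. No text states the subtraction, and Scenario C shows that a blanket subtraction works only if every control answered in the same way. Nor does the protocol's four-appointment schedule say that the enrolment visit is logged as attended. Under the SAP, the app is downloaded at enrolment and plans the later appointments.

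**Conclusion.** The primary outcome has two incompatible definitions, and the protocol contains both. That much needs no assumption.

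The consequence is conditional. If the SAP's three-visit count in the reminder arm meets unrestricted recall in the controls, the baseline visit alone can raise the control mean by up to 1.0 visit, twice the 0.5-visit target. The effect is masked entirely when half of the controls include the visit, and reversed in sign beyond that. This rests on no reminder-arm woman counting the visit and on a q that the documents do not give. If all arms include the visit, the mean difference and the ANOVA are unaffected, and only the percent increase is diluted (33% to 20% at an assumed control mean of 1.5).

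One visit is the limit for the baseline visit alone. An open recall question could also collect visits outside the schedule. The ambiguity should be removed before data collection, because a recalled total cannot later be split into women who counted the first visit and women who did not.

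**What to change.** 1. State one primary outcome in both documents: how many of the three scheduled check-ups after the baseline visit were attended, scored 0 to 3. This follows the definition already in SAP section 7 and in the protocol's Primary Outcome paragraph.
2. Bring the rest into line with it: the four-appointment measure in the protocol's Outcome Measures, the four-appointment reminder-arm description and the informed-control question in Arms and Interventions, and the control-arm contact text in SAP section 6.2.
3. In the 6-month call of every arm that is contacted, including the reminder arm, ask the same dated question: since the first visit on the enrolment date, which of the three later check-ups were attended?
4. Exclude the enrolment-date visit from every chart count, including any made for the uninformed control arm.
5. Reconcile the data source for the uninformed arm across SAP sections 6.1 and 6.2 and the protocol's arm description, since a call question cannot reach women who gave no contact information.

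The cost is wording in the protocol, the SAP, the call script and the chart abstraction rule. Items 1 to 4 need no extra patients or staff.
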